4.5.3.4 Exposure adjusted analysis

Exposure adjusted incidence rate of ARIA-E events will be summarized based on safety MRI data. The exposure adjusted follow-up time is from the first dose until the initial occurrence of ARIA-E for those who experienced ARIA-E, and until the end of follow-up for those who did not. Since ARIA is an MRI finding, the day of the last MRI assessment in the placebo-controlled period will be used as the end of follow-up for those who didn't experience the event.

Study drug administration information prior to first ARIA-E onset will be summarized for ARIA-E subjects, including number of total infusions, number of infusions at each dose level (placebo, 1 mg/kg, 3 mg/kg, 6 mg/kg and 10 mg/kg), dose level of the last infusion, maximum dose level received, and cumulative dose as a continuous variable.

4.5.3.5 Time to event analysis

Kaplan-Meier plot of time to first ARIA-E event will be produced based on safety MRI data. Time to event is calculated as date of the MRI assessment that initially detects ARIA-E event - date of first infusion (aducanumab or placebo) +1. Censor time for subjects without ARIA-E is calculated as date of last MRI assessment in the placebo-controlled period - date of first infusion (aducanumab or placebo) +1. Estimated proportion with ARIA-E and number of subjects at risk at selected timepoints will also be presented. The plot will be presented by treatment group stratified by ApoE status.

4.5.3.6 Subgroup analysis for protocol version 4

Due to the change in maximal dose from 6 mg/kg to 10 mg/kg for ApoE ϵ 4 carrier high dose group in protocol version 4, not all subjects have had opportunity to receive the protocol specified high dose (6 doses in titration before receive 10mg/kg) in the placebo-controlled period. Incidence of ARIA events and summary of first ARIA-E events tables will be provided for ApoE ϵ 4 carriers who were randomized to the high dose group, stratified by the expected number of doses at 10 mg/kg (categories of 0, 1-6, 7-13, 14, and a total column of having at least one dose) a subject would have received based on the first infusion date and the date consenting to protocol version 4. Randomization treatment groups will be used for this analysis.

4.5.4 Clinical Laboratory Data

The following clinical laboratory parameters are assessed in the protocol and will be analyzed:

- Hematology:
 - White blood cells (leukocytes), lymphocytes, neutrophils, monocytes, eosinophils, basophils
 - Red blood cells (erythrocytes), erythrocytes distribution width, erythrocytes mean corpuscular volume, erythrocytes mean corpuscular hemoglobin, erythrocytes mean corpuscular hemoglobin concentration

CONFIDENTIAL

The information contained herein may not be used, disclosed, or published without the written consent of Biogen MA Inc.

- Hemoglobin
- Hematocrit
- Platelet count
- Blood chemistry:
 - Liver: alanine aminotransferase (ALT), aspartate aminotransferase (AST), alkaline phosphatase (ALP), total bilirubin, direct bilirubin, gamma-glutamyl-transferase (GGT)
 - Renal: blood urea nitrogen (BUN), creatinine
 - Electrolytes: sodium, potassium, chloride, bicarbonate
 - Other: glucose, calcium, phosphorus, albumin, uric acid, lactate dehydrogenase (LDH), total protein
- Urinalysis: specific gravity, potential of hydrogen (pH), color, blood, glucose, ketones, protein, white blood cells, red blood cells

4.5.4.1 Quantitative analyses

For numeric laboratory parameters, actual values, change from baseline and percent change from baseline will be summarized by visit. Number of evaluable subjects, mean, standard deviation, median, 25% and 75% quartiles, minimum and maximum values will be presented at each visit.

Plots of mean values (with standard error) for numeric laboratory parameters at each visit will be provided.

Listings of individual laboratory measurements by patients for all the parameters will be provided.

Visit windows for by visit summaries

For laboratory by visit summaries, the analysis visit should be defined using visit windows (see Table 7 below). If there is more than 1 value in the same analysis visit window for a certain parameter for a subject, then the closest record to the target visit day will be used for the by visit analysis. If there are 2 values in the same analysis visit window with the same distance from the target visit day for a certain parameter for a subject, then the record with the later date will be used for the by visit analysis. If there are 2 values on the same day for a certain parameter for a subject, then the record with the later time will be used for the by visit analysis.

Table 7: Visit Windows for Laboratory by Visit Summaries

Analysis visit	Target visit day	Analysis visit window
Baseline	1	Most recent non-missing pre-dose value
Week 24	169	[2, 252]
Week 48	337	[253, 420]
Week 72	505	[421, 525]

CONFIDENTIAL

The information contained herein may not be used, disclosed, or published without the written consent of Biogen MA Inc.

Analysis visit	Target visit day	Analysis visit window
Week 78	547	[526, the end day of the placebo-controlled period*]
* The end day of the placebo-controlled period is the last day before the first infusion in LTE for subjects who enter LTE, and is the last day in study for subjects who do not enter LTE.		

4.5.4.2 Qualitative analyses

For all qualitative analyses, all values will be included (not just the “analyzed record” within each visit window in the quantitative analyses).

Shift analyses

Laboratory data will be summarized using shift tables where appropriate. Each subject’s hematology, blood chemistry and urinalysis numeric values will be flagged as “low”, “normal”, or “high” relative to the normal ranges of the central laboratory or as “unknown” if no result is available. Each subject’s urinalysis categorical values will be flagged as “positive” or “negative”, or “unknown” if no value is available.

Shifts from baseline to high/low status will be presented for hematology, blood chemistry and urinalysis numeric parameters, and shifts from baseline to abnormal (positive) will be presented for urinalysis categorical parameters. Shift to low includes normal to low, high to low, and unknown to low; Shift to high includes normal to high, low to high, and unknown to high. Subjects need to have at least one post-baseline evaluation and a baseline value not low or high or positive (including missing) in order to be included in the analysis. A listing of laboratory normal ranges will be provided.

Grade analyses

Worst post-baseline grade will be summarized for each laboratory parameter in both exclusive way and cumulative way. Subjects need to have at least one post-baseline evaluation in order to be included in the analysis. Common Toxicity Criteria for Adverse Events v4.0.3 (CTCAE) published on 2010-06-14 will be used for grade determination. Grade determination is based solely on laboratory values not taking AEs into account.

Potentially Clinically Significant laboratory abnormalities analyses

For hematology, blood chemistry and urinalysis, the number of subjects with potentially clinically significant laboratory abnormalities post-baseline will be summarized for the parameters provided in Table 8. Subjects need to have at least one post-baseline evaluation and a baseline value not potentially clinically significant (including missing) in order to be included in the analysis.

Table 8: Criteria to Determine Potentially Clinically Significant (PCS) Laboratory Abnormalities

Clinical Laboratory Outlier Criteria		
Parameter name	PCS Low	PCS High
HEMATOLOGY		

CONFIDENTIAL

The information contained herein may not be used, disclosed, or published without the written consent of Biogen MA Inc.

Clinical Laboratory Outlier Criteria		
Parameter name	PCS Low	PCS High
White blood cells	<3.0 x 10 ⁹ /L	>16 x 10 ⁹ /L
Lymphocytes	<0.8 x 10 ⁹ /L	>12 x 10 ⁹ /L
Neutrophils	<1.5 x 10 ⁹ /L	>13.5 x 10 ⁹ /L
Monocytes	N/A	>2.5 x 10 ⁹ /L
Eosinophils	N/A	>1.6 x 10 ⁹ /L
Basophils	N/A	>1.6 x 10 ⁹ /L
Red blood cells	≤3.5 x 10 ¹² /L	≥6.4 x 10 ¹² /L
Hemoglobin - Females	≤95 g/L	≥175 g/L
Hemoglobin - Males	≤115 g/L	≥190 g/L
Hematocrit - Females	≤32%	≥54%
Hematocrit - Males	≤37%	≥60%
Platelet count	≤75 x 10 ⁹ /L	≥700 x 10 ⁹ /L
BLOOD CHEMISTRY		
Alanine aminotransferase (ALT)	N/A	>3 x ULN
Aspartate aminotransferase (AST)	N/A	>3 x ULN
Alkaline phosphatase (ALP)	N/A	>3 x ULN
Total bilirubin	N/A	>1.5 x ULN
Blood urea nitrogen (BUN)	N/A	≥10.7 mmol/L
Creatinine	N/A	≥176.8 umol/L
Sodium	≤126 mmol/L	≥156 mmol/L
Potassium	≤3 mmol/L	≥6 mmol/L
Chloride	≤90 mmol/L	≥118 mmol/L
Bicarbonate	≤16 mmol/L	≥35 mmol/L
Glucose	≤2.2 mmol/L	≥9.7 mmol/L
Calcium	≤2 mmol/L	≥3 mmol/L
Phosphorus	≤0.6 mmol/L	≥1.7 mmol/L
Albumin	≤25 g/L	≥625 g/L
Total protein	≤45 g/L	≥100 g/L
URINALYSIS		
Glucose	N/A	≥ ++++
Ketones	N/A	≥ ++++
Protein	N/A	≥ ++
ULN = upper limit of normal		

Potential serious hepatotoxicity

Potential serious hepatotoxicity is defined as ALT or AST > 3x ULN and total bilirubin > 2x ULN at any time post-baseline, not necessarily concurrent. A scatterplot of the maximum post-baseline ALT or AST value relative to ULN and maximum post-baseline total bilirubin value relative to ULN (not necessarily concurrent) for each subject will be provided. A line plot of ALT, AST, ALK and total bilirubin values over time for subjects with potential serious hepatotoxicity will be provided. In addition, subjects with ALT > 1x ULN, >3x ULN, >5x ULN, >10x ULN or >20x ULN, subjects with AST > 1x ULN, >3x ULN, >5x ULN, >10x ULN or >20x ULN, subjects with total bilirubin >1x ULN or >2x ULN, subjects with ALP >1x ULN or >1.5x ULN, and subjects with AST or ALT > 3x ULN post-baseline accompanied by concurrently elevated total bilirubin >1.5x ULN or > 2x ULN will be presented. Concurrent is defined as on the same day. A listing of subjects with potential serious hepatotoxicity will be provided.

CONFIDENTIAL

The information contained herein may not be used, disclosed, or published without the written consent of Biogen MA Inc.

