4.5.2 Clinical Adverse Events

Treatment-emergent AEs (TEAEs)

All AEs will be analyzed based on the principle of treatment emergence. A treatment-emergent AE was defined as an AE that started or worsened after the start of first infusion of study treatment.

To define treatment emergence for AEs with missing start or stop date or time the following additional criteria will be used:

- if both the start and stop dates for a particular AE are missing, then that AE is considered treatment emergent;
- if the start date for a particular AE is missing and the stop date/time falls after the first dose date/time, then that AE is considered treatment emergent;
- if the start date for a particular AE was the same as the first dose date, and the start time was missing, then that event is considered treatment emergent.

For AEs with a partial start date, the year/month of the event date will be compared to that of the first dosing date to determine whether the event is treatment emergent.

In addition, SAEs that occurred since a subject was screened in the study and prior to the first infusion of study treatment, which by definition are not treatment-emergent, will be analyzed separately.

Only TEAEs will be included in the AE tables, unless otherwise specified. Listings of AEs will include all events, whether treatment-emergent or not.

As specified in the protocol, subjects were expected to return to the study site for an End of Study visit 18 weeks after the last administration of study treatment. However, some subjects may elect to continue study participation on a modified schedule after discontinuing treatment, possibly in substantial excess of 18 weeks. For most general AE summaries, AEs

CONFIDENTIAL

The information contained herein may not be used, disclosed, or published without the written consent of Biogen MA Inc.

with an onset more than 18 weeks after the last dose will be excluded (will specify in the footnote of the specific table). For incidence rate analyses excluding AEs more than 18 weeks after the last dose, the “last day on study” in follow-up time calculation will be replaced with “18 weeks after last dose or last day on study, whichever earlier”. Summaries of deaths and AEs leading to study withdrawal, and other selected analyses will include all AEs regardless of the time since the last dose. Listings will include all AEs, unless otherwise specified.

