4.5.5 C-SSRS Data

The Columbia Suicide Severity Rating Scale (C-SSRS) is an assessment that evaluates suicidal ideation and behavior. There are 5 “Yes/No” questions on suicidal ideation following the increasing severity order: (1) Wish to be dead, (2) Non-specific active suicidal thoughts, (3) Active suicidal ideation with any methods (not plan) without intent to act, (4) Active suicidal ideation with some intent to act, without specific plan, (5) Active suicidal ideation with specific plan and intent, and 6 “Yes/No” questions on suicidal behavior following the increasing severity order: (6) Preparatory acts or behavior, (7) Aborted attempt, (8) Interrupted attempt, (9) Actual attempt, (10) Suicidal behavior, (11) Suicide (only at post-baseline visits). Another “Yes/No” question of whether the subject has engaged in non-suicidal self-injurious behavior is also collected.

In the summary table for C-SSRS, number of subjects who answered “Yes” to each of the 11 questions post-baseline, subjects who answered “Yes” to at least one question for suicidal ideation, subjects who answered “Yes” to at least one question for suicidal behavior, and subjects who have engaged in non-suicidal self-injurious behavior will be presented. A listing of subjects with any suicidal ideation or behavior at baseline or post-baseline will be provided.

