4.5.6 ECG Data

Shift from normal or unknown ECG at baseline to abnormal, not adverse event or abnormal, adverse event post-baseline ECG will be summarized for the placebo-controlled period. Subjects with abnormal post-baseline ECG status will be listed.

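### The C-SSRS summary, and to a lesser degree the CTCAE laboratory grade table, cannot separate findings already present at baseline from new or worsened ones

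*SAP*

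**What the plan says.** **C-SSRS.** Section 4.5.5 of the placebo-controlled SAP tabulates subjects answering positively "to each of the 11 questions post-baseline", subjects with at least one positive ideation item, subjects with at least one positive behaviour item, and subjects with non-suicidal self-injury. The post-baseline restriction is written only against the item counts. Baseline answers are collected: only item 11 is confined to post-baseline visits, and the listing covers subjects positive at baseline or later. Section 3.5.5 of the LTE SAP uses the same counts for the active-treatment period.

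**Laboratory grades.** Section 4.5.4.2 states: "Worst post-baseline grade will be summarized for each laboratory parameter in both exclusive way and cumulative way". The entry rule is "Subjects need to have at least one post-baseline evaluation in order to be included in the analysis". LTE SAP section 3.5.4.2 has the same design, with the evaluation falling in the active-treatment period.

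**Displays that use baseline.** The shift analysis requires "a baseline value not low or high or positive (including missing) in order to be included in the analysis". The PCS analysis requires "a baseline value not potentially clinically significant (including missing) in order to be included in the analysis". For adverse events, section 4.5.2 says "All AEs will be analyzed based on the principle of treatment emergence" and defines the term: "A treatment-emergent AE was defined as an AE that started or worsened after the start of first infusion of study treatment". For ECGs, section 4.5.6 says "Shift from normal or unknown ECG at baseline to abnormal, not adverse event or abnormal, adverse event post-baseline ECG will be summarized".

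**The concern.** A subject with grade 2 before dosing and an unchanged grade 2 afterwards enters the grade table exactly as does a subject who rose from grade 0 to grade 2. A subject who reported a wish to be dead at baseline and reports it again enters the C-SSRS table exactly as does a subject reporting it for the first time. A safety reader needs that distinction. Carried-over findings should be balanced by randomisation unless the drug acts on them, so they do not create a false drug effect. They add a similar count to each arm and make a true relative increase in new findings look smaller.

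For C-SSRS, no tabulated result answers the question. For laboratory data, the grade table is the only graded severity summary in the plan, and it cannot show worsening.

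**Working it through.** **Step 1. Counting rules side by side (placebo-controlled SAP).**

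| Display | Section | Baseline condition |
|---|---|---|
| Adverse events | 4.5.2 | Onset or worsening after first infusion |
| Laboratory shifts | 4.5.4.2 | Not already abnormal; missing allowed |
| PCS values | 4.5.4.2, Table 8 | Not already PCS; missing allowed |
| ECG | 4.5.6 | Normal or unknown |
| CTCAE grades | 4.5.4.2 | None |
| C-SSRS | 4.5.5 | None |
| Liver tests by multiple of ULN | 4.5.4.2 | None |
| Vital signs, absolute limits | 4.5.7, Table 9 | None (change criteria sit beside them) |

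**Step 2. What the other displays recover.** For C-SSRS, only the listing.

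For laboratory data, the shift table shows new abnormalities. The PCS table shows crossings of its threshold by subjects not beyond it at baseline. Section 4.5.4.1 gives change from baseline by visit. A subject already high at baseline cannot be counted as a shift to high. If the parameter has no Table 8 criterion (GGT, LDH and uric acid are listed in 4.5.4 but absent from Table 8), the PCS table cannot show that subject's worsening either. The by-visit summaries and individual listings remain.

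**Step 3. Direction and size.** The SAP states no figure on this point, so there is none to reproduce. Let b be the proportion with the finding at baseline, r the share of those who still show it afterwards (equal in both arms), and p the new-onset risk among the rest. All three are assumptions.

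- Reported proportion = b·r + (1 − b)·p
- Reported risk difference = (1 − b)·(p1 − p0)

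Laboratory grade 1 or above, p = 5% v 10% (true ratio 2.00), r = 0.8:

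| b | Lower-risk arm | Higher-risk arm | Ratio | Difference (points) |
|---|---|---|---|---|
| 2% | 0.016 + 0.049 = 6.5% | 0.016 + 0.098 = 11.4% | 1.75 | 4.9 |
| 5% | 0.040 + 0.0475 = 8.75% | 0.040 + 0.095 = 13.5% | 1.54 | 4.75 |
| 10% | 0.080 + 0.045 = 12.5% | 0.080 + 0.090 = 17.0% | 1.36 | 4.5 |
| 20% | 0.160 + 0.040 = 20.0% | 0.160 + 0.080 = 24.0% | 1.20 | 4.0 |

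Varying r from 0.5 to 1.0 gives ratios of 1.83 to 1.71 at b = 2%, and 1.29 to 1.17 at b = 20%.

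C-SSRS ideation, p = 3% v 6% (true ratio 2.00):

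| b | Ratio, r = 0.3 | Ratio, r = 0.6 |
|---|---|---|
| 1% | 1.91 | 1.83 |
| 3% | 1.76 | 1.62 |
| 5% | 1.66 | 1.49 |
| 10% | 1.47 | 1.31 |

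For example, at b = 5% and r = 0.6: 0.030 + 0.0285 = 5.85% v 0.030 + 0.057 = 8.7%, ratio 1.49.

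**Step 4. Where the effect is weak or changes.**

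- *High grades.* Assume 0.2% at grade 3 or above at baseline, all persisting. Assume a risk of reaching grade 3 of 2% v 8% from grades 1–2 and 0.5% v 2% from grade 0. The ratio falls from 4.0 to 3.29 with 10% at grades 1–2 at baseline, or to 3.40 with 20%. The risk difference is unchanged.
- *Drug raises persistence.* With r = 0.6 v 0.8 and the 5% v 10% onset rates, the ratio is 1.74 at b = 5% and 1.50 at b = 20%. The risk difference rises to 5.8 and 8.0 points.

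**The case against.** The strongest reply is that nothing here is an error. Both tables are labelled for what they count, and neither promises treatment emergence. They are descriptive with no planned test, so a comparison of statistical power would describe an analysis that the plan does not contain. The grade table also complements the others: a move from grade 1 to grade 3 can be lost from the shift table but appears in the grade table. For C-SSRS, numbers may be small enough for a reader to work from the listing. Carry-over depends on a recall period that the SAP does not state, and a later positive behaviour item may be a new act rather than a carried-over state.

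Most of this stands, and it limits the point to a reporting matter. It does not give the reader a tabulated count of new or worsened ideation, or a way to tell an unchanged grade from a worsened one.

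Three stronger readings are tempting, and the document supports none of them:

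- *That a drug-related rise in laboratory toxicity would be hidden.* The shift, PCS and change-from-baseline displays show new abnormalities.
- *That these two tables are the only exceptions to a uniform rule.* The liver threshold counts and the absolute vital-sign limits also have no baseline condition.
- *That late-start subjects have no suitable baseline in the extension.* LTE SAP section 3.5.1 defines one for active-treatment-period analyses. What is missing is its use as a comparator in these two tables.

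**Conclusion.** The point holds as a minor one. It is stronger for C-SSRS, where no summary takes baseline into account. It is weaker for laboratory grades, where the remaining gap is worsening in subjects already abnormal at baseline, chiefly for parameters without a PCS criterion. With similar carry-over in each arm, risk ratios move towards 1, mainly at low grades. Under the assumed rates, a ratio of 2.0 is reported as anything from 1.91 (C-SSRS, 1% positive at baseline, 30% persisting) to 1.17 (laboratory, 20% abnormal at baseline, all persisting). The true size cannot be fixed from the SAP and is small when baseline prevalence is low. No planned test or efficacy conclusion is affected.

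**What to change.** Keep every all-post-baseline count and add the following:

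1. **C-SSRS (4.5.5; LTE 3.5.5).** Among subjects with at least one post-baseline C-SSRS, add a row for new or worsened ideation (none, or a less severe level, at baseline) and a row for behaviour in subjects with none at baseline. Continue to report any post-baseline behaviour in full, because a rule requiring greater severity than baseline would miss a new attempt in a subject with an earlier one. State that the ideation, behaviour and self-injury counts are post-baseline.
2. **Laboratory grades (4.5.4.2; LTE 3.5.4.2).** Present worst post-baseline grade by baseline grade, taking a missing baseline as grade 0, or add a count of subjects whose grade increased.
3. **LTE tables.** For late-start subjects, use the LTE baseline already defined in LTE section 3.5.1 as the comparator in both displays.

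The cost is SAP wording and a few table rows or columns. No new data are needed.

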3.5.4.2 Qualitative analyses

For qualitative analyses, all values will be included (not just the “analyzed record” within each visit window in the quantitative analyses).

Shift analyses

Laboratory data will be summarized using shift tables where appropriate for the placebo-controlled and LTE active treatment period. Each subject's hematology, blood chemistry and urinalysis numeric values will be flagged as "low", "normal", or "high" relative to the normal ranges of the central laboratory or as "unknown" if no result is available. Each subject's urinalysis categorical values will be flagged as "positive" or "negative", or "unknown" if no value is available.

Shifts from baseline to high/low status will be presented for hematology, blood chemistry and urinalysis numeric parameters, and shifts from baseline to abnormal (positive) will be presented for urinalysis categorical parameters. Shift to low includes normal to low, high to low, and unknown to low; Shift to high includes normal to high, low to high, and unknown to high. Subjects need to have at least one post-baseline evaluation and a baseline value not low or high or positive (including missing) in order to be included in the analysis.

For early start subjects, the placebo-controlled baseline will be used and shifts that occurred in either placebo-controlled or LTE period will be included. For late start subjects, the LTE baseline will be used and shifts that occurred in the LTE period based on LTE baseline will be included.

Grade analyses

Worst post-baseline grade will be summarized for each laboratory parameter in both exclusive way and cumulative way for the placebo-controlled and LTE active treatment period. Subjects need to have at least one post-baseline evaluation in the active treatment period in order to be included in the analysis. Common Toxicity Criteria for Adverse Events v4.0.3 (CTCAE) published on 2010-06-14 will be used for grade determination. Grade determination is based solely on laboratory values not taking AEs into account.

Potentially Clinically Significant laboratory abnormalities analyses

Please refer to the placebo-controlled SAP for the parameters and criteria for potentially clinically significant laboratory abnormalities analyses.

The number of subjects with potentially clinically significant laboratory abnormalities post-baseline will be summarized for the placebo-controlled and LTE active treatment period.

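### Table 8 sets the high albumin limit at 625 g/L, which no valid serum sample can reach, so the PCS-high albumin row is empty whatever the data

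*SAP*

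**What the plan says.** Section 4.5.4 of the placebo-controlled SAP lists albumin and total protein in the same blood chemistry panel. Section 4.5.4.2 then plans a PCS analysis in which "the number of subjects with potentially clinically significant laboratory abnormalities post-baseline will be summarized for the parameters provided in Table 8". The two relevant rows of Table 8 are "Albumin ≤25 g/L ≥625 g/L" and "Total protein ≤45 g/L ≥100 g/L". In each row the first figure is the PCS-low limit and the second the PCS-high limit. No footnote or other section gives another albumin limit or unit.

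The LTE SAP sets no limits of its own. Its section 3.5.4.2 says: "Please refer to the placebo-controlled SAP for the parameters and criteria for potentially clinically significant laboratory abnormalities analyses". The albumin limit therefore governs both analyses.

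**The concern.** The high limit for a component lies far above the high limit for the whole, in the same table and unit. The low limits are in the expected order (albumin 25, total protein 45), but the high limits are reversed (albumin 625, total protein 100).

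A limit that cannot be reached turns a safety count into a constant. The table would show zero PCS-high albumin cases in each arm, and a reader would take that as an observation when the threshold has fixed it in advance. The same criterion also decides who is eligible for the count, since subjects already PCS at baseline are left out. With this limit nobody can be left out for a high baseline albumin.

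**Working it through.** The 625 g/L is a fixed table entry, not a derived figure, so there is no calculation of the plan's own to reproduce. The check compares it with the other limits in Table 8.

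**Step 1. Component against whole.**

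- Albumin high limit / total protein high limit = 625 / 100 = 6.25.
- Albumin low limit / total protein low limit = 25 / 45 = 0.56.

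In any one sample, albumin ≤ total protein. Albumin ≥625 g/L therefore implies total protein ≥625 g/L. The 100 g/L limit is a flag and not a ceiling, so the ratio of 6.25 does not by itself prove impossibility. It shows that the two limits are inconsistent. The impossibility comes from basic physiology: total protein in serum does not approach 625 g/L.

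**Step 2. Spread between limits, as corroboration only.** High/low ratios of the two-sided chemistry rows in Table 8:

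| Parameter | High / low | Ratio |
|---|---|---|
| Sodium | 156 / 126 | 1.24 |
| Chloride | 118 / 90 | 1.31 |
| Calcium | 3 / 2 | 1.50 |
| Potassium | 6 / 3 | 2.00 |
| Bicarbonate | 35 / 16 | 2.19 |
| Total protein | 100 / 45 | 2.22 |
| Phosphorus | 1.7 / 0.6 | 2.83 |
| Glucose | 9.7 / 2.2 | 4.41 |
| **Albumin** | **625 / 25** | **25.0** |

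Albumin is 25 / 4.41 = 5.7 times the next largest chemistry ratio. Some hematology rows are wider: lymphocytes 12 / 0.8 = 15.0, platelets 700 / 75 = 9.33, neutrophils 13.5 / 1.5 = 9.0, white cells 16 / 3.0 = 5.33. Against the whole table albumin is still the largest, by 25 / 15 = 1.7 times.

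**Step 3. A dropped decimal point, as an assumption.** With 62.5 g/L the ratio to the albumin low limit is 62.5 / 25 = 2.5, close to the 2.22 for total protein. The ratio to the total protein high limit is 62.5 / 100 = 0.625, in line with the 0.56 on the low side. Both orderings would then be coherent. The documents do not state that 62.5 was meant.

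**Step 4. What the limit feeds.** It feeds one PCS-high row in the placebo-controlled table and one in the LTE table. The expected entry in both is 0 in all groups for valid data. The documents give no albumin distribution, so the count under a corrected limit cannot be computed and may itself be near zero.

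**The case against.** There are four points on the other side.

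- **Reading artefact.** The text was read from a PDF by a program, and a lost decimal point is the kind of single-character change that can result. If so, the plan contains no error. This cannot be fully excluded. It is unlikely, because other decimals in the same table survive (10.7, 176.8, 2.2, 9.7, 0.6, 1.7).
- **The ratio comparison is weak.** High/low ratios differ by analyte, and the factor of 5.7 holds only among chemistry rows. This is fair, and the ratios are offered as support only. The argument rests on albumin being part of total protein.
- **Zero is too absolute.** The qualitative analyses use all recorded values, so a unit or data-entry error could trip the flag. This also stands: the count is zero for any valid result, and an entry in that row would point to a data error.
- **The consequence is slight.** High albumin stays visible elsewhere. Section 4.5.4.2 states that "Shifts from baseline to high/low status will be presented for hematology, blood chemistry and urinalysis numeric parameters", and section 4.5.4.1 gives by-visit maxima and adds that "Listings of individual laboratory measurements by patients for all the parameters will be provided". The LTE SAP has matching shift tables, maxima and listings. This stands too. It settles the priority of the point but does not make the number right.

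**Conclusion.** The concern holds. The PCS-high limit for albumin is wrong as written: it is 6.25 times the total protein high limit in the same table and cannot be met by a valid sample. One row in each of two safety tables therefore carries no information.

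The conclusion needs only the physiological fact in step 1 and the assumption that the figure was read correctly from the PDF. Because of that second assumption, confidence is moderate. The correction is desirable, not essential: no efficacy, ARIA or hepatotoxicity analysis depends on this cell.

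**What to change.** Ask the sponsor to confirm the intended albumin high limit, then do one of the following in Table 8 of the placebo-controlled SAP:

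- replace 625 g/L with a reachable limit below 100 g/L (62.5 g/L if a dropped decimal point is confirmed); or
- enter N/A if no high limit is wanted, as the table already does for limits it does not use.

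The LTE SAP takes over the correction through its cross-reference and needs no change of text. The cost is one table cell and the matching threshold in the analysis program. Data collection is unaffected.
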